# 9.1. REQUIREMENTS

The table below summarizes the requirements for recording safety events on the case report form and for reporting safety events on the non-interventional study (NIS) adverse event monitoring (AEM) Report Form to Pfizer Safety. These requirements should be described for the following 3 types of events.(1) serious adverse events (SAEs); (2) non-serious AEs (as applicable); and (3) scenarios involving exposure to a Pfizer product, including exposure during pregnancy, exposure during breast feeding, medication error, overdose, misuse, extravasation, and occupational exposure. These events are defined in the section "Definitions of safety events".

Safety event	Recorded on the case report form	Reported on the NIS AEM Report Form to Pfizer Safety within 24 hours of awareness
SAE	All	All
Non-serious AE	All	None

Safety event	Recorded on the case report form	Reported on the NIS AEM Report Form to Pfizer Safety within 24 hours of awareness
Scenarios involving exposure to a Pfizer product, including exposure during pregnancy, exposure during breast feeding, medication error, overdose, misuse, extravasation; lack of efficacy; and occupational exposure	All (regardless of whether associated with an AE), except occupational exposure	All (regardless of whether associated with an AE) involving exposure to a Pfizer product

For each AE, the investigator must pursue and obtain information adequate both to determine the outcome of the adverse event and to assess whether it meets the criteria for classification as a SAE (see section "Serious Adverse Events" below)

Safety events must be reported to Pfizer within 24 hours of awareness of the event by the investigator as described in the table above. In particular, if the SAE is fatal or life-threatening, notification to Pfizer must be made immediately, irrespective of the extent of available event information. This timeframe also applies to additional new (follow-up) information on previously forwarded safety event reports. In the rare situation that the investigator does not become immediately aware of the occurrence of a safety event, the investigator must report the event within 24 hours after learning of it and document the time of his/her first awareness of the events.

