# 9.2. Reporting period

For each patient, the safety event reporting period begins at the time of the patient's first dose of this product, and lasts through the end of the observation period of the study, which must include at least 28 calendar days following the last administration of a drug under study; a report must be submitted to Pfizer Safety (or its designated representative) for any of the types of safety events listed in the table above occurring during this period. If a patient was administered a drug under study on the last day of the observation period, then the reporting period should be extended for 28 calendar days following the end of observation.

If the investigator becomes aware of a SAE occurring at any time after completion of the study and s/he considers the SAE to be related to this product, the SAE also must be reported to Pfizer Safety.

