# 9.3. Causality assessment

The investigator is required to assess and record the causal relationship. For all AEs, sufficient information should be obtained by the investigator to determine the causality of each adverse event. For AEs with a causal

relationship to this product, follow-up by the investigator is required until the event and/or its sequelae resolve or stabilize at a level acceptable to the investigator, and Pfizer concurs with that assessment.

An investigator's causality assessment is the determination of whether there exists a reasonable possibility that this product caused or contributed to an adverse event. If the investigator's final determination of causality is "unknown" and s/he cannot determine whether this product caused the event, the safety event must be reported within 24 hours.

If the investigator cannot determine the etiology of the event but s/he determines that this product did not cause the event, this should be clearly documented on the case report form and the NIS AEM Report Form.

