8.2.3. Safety Analysis

Adverse drug reactions and adverse events observed during the observation period (from the day of initiation of Vfend treatment to the day of completion of treatment) + follow-up period (28 days*) will be tabulated. If the duration of the observation period + follow-up period is beyond October 31, 2018, events observed by October 31, 2018 will be tabulated. All events reported in this study will be included in listings.

*: The duration of the follow-up period in this study was set at 28 days because a 30-day follow-up period was provided in a clinical study and the period of collection of adverse events using NIS AE Report Form in this study is up to 28 days after the day of completion of treatment.

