- Change in treatment with Vfend: If multiple types of change in treatment with Vfend are reported, one of discontinuation, temporarily discontinued, dose reduction, dose increase or no change, in descending order of precedence, will be adopted.
- Outcome: The outcome of the last occurring event will be used.
- Safety specifications

The number and proportion of patients with events will be tabulated. In addition, the number and proportion of patients with safety specifications by change in treatment with Vfend and outcome will be tabulated by SOC and PT.

• Major investigation items

The number and proportion of patients with major investigation items will be tabulated by SOC and PT. In addition, the number and proportion of patients with major investigation items will be tabulated by SOC and PT for each of the following items.

- Change in treatment with Vfend [discontinuation, temporarily discontinued, dose reduction, dose increase, no change]
- Outcome [not recovered, recovered with sequela, recovering, resolved/recovered, unknown]
- Age (1) [<15 years, ≥ 15 years]

Furthermore, in order to examine the difference between patients who discontinued treatment and those who did not by major investigation item, patients with major investigation items will be tabulated by patient background factor, status of discontinuation/completion, concomitant medication, and status of administration.

• Timing of onset of adverse drug reactions

The number of patients with adverse drug reactions will be tabulated by SOC and PT by timing of initial onset of adverse drug reactions. Categories of timing of onset will be every 30 days. However, if there are many adverse drug reactions that occur at an early stage, the analysis will be performed by subdividing the category of the first 30 days as necessary. Major investigation items will be analyzed in the same manner.

For major investigation items, time to event onset will be summarized for each patient in accordance with Section 8.1.4 with the initial onset of the major investigation item considered as an event. Patients without adverse drug reactions will be right-censored after the observation period + follow-up period (28 days) of this study.

• Relationship between concomitant medications and development of adverse drug reactions

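### Time to onset of the major investigation items is censored past the 31 October 2018 limit on events, and onsets after the last dose have no change-in-treatment level

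*SAP*

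**What the plan says.** **Events.** SAP 8.2.3 tabulates adverse events and reactions over the observation period plus 28 days, with a calendar limit: "If the duration of the observation period + follow-up period is beyond October 31, 2018, events observed by October 31, 2018 will be tabulated".

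**Censoring.** For each major investigation item (hepatic toxicity, visual events), SAP 8.2.3.1 summarises time to first onset by Kaplan-Meier: "Patients without adverse drug reactions will be right-censored after the observation period + follow-up period (28 days) of this study". No calendar limit appears there.

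**Change in treatment.** SAP 8.2.3.1 tabulates the major items by five levels: discontinuation, temporary discontinuation, dose reduction, dose increase, no change. It then compares patients who discontinued with those who did not. SAP 8.2.3.3 splits the liver-test summaries by change in treatment. SAP 7 adds 'unknown', for missing values only.

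**Collection after the last dose.** Protocol 7.2.6 ends observation on the day treatment is completed, or follows patients still on drug to the end of the investigation period. Protocol 7.3.7 records adverse events to the end of observation. Protocol 9.2 describes a reporting period through the end of observation, "which must include at least 28 calendar days following the last administration of a drug under study". Reports are due, it says, "for any of the types of safety events listed in the table above occurring during this period". It adds 28 days if the patient was dosed on the last observation day. SAP 8.2.3 bases its 28 days on two reasons. One is that an earlier trial followed patients for 30 days. The other concerns the reporting form: "the period of collection of adverse events using NIS AE Report Form in this study is up to 28 days after the day of completion".

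**The concern.** Kaplan-Meier requires that anyone counted as at risk on a day could have been counted as an event on that day. Under the literal rule this fails at the calendar end of the study. A patient still on drug on 31 October 2018 would be censored on 28 November 2018, although nothing after 31 October counts. The curve is then too low and its quartiles too late.

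The sentence also describes the wrong group. The event is the first major item, but the censoring time is given for patients with no adverse drug reaction at all. A patient with, say, only a rash has neither an event nor a stated censoring time.

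The classification gap matters more for interpretation. Protocol 7.3.8 and SAP 2.1 make the comparison of patients who could continue with those who had to stop the purpose of the major items. An onset after the last dose cannot have changed the treatment. With no level for it, one site may enter 'no change', another 'discontinuation', and a third may leave the field blank. These cases would then be spread arbitrarily over the groups being compared.

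**Working it through.** **1. The plan's own figure.** Protocol 7.5.2 takes 200 patients and 20% hepatic toxicity and expects at least 31 cases with about 95% probability. Exact binomial: P(X ≥ 31) = 0.957 and P(X ≥ 32) = 0.937. It reproduces. The expected number is 200 × 0.20 = 40, used below.

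**2. Dates.** 31 October 2018 − 28 days = 3 October 2018, so observation ending 4 to 31 October gives 1 to 28 days at risk with no countable event. The latest literal censoring date is 31 October + 28 days = 28 November 2018.

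**3. Assumptions.** The documents give no treatment durations or registration dates by patient. I assume exponential treatment duration with median M = 30, 60, 90 or 180 days (rate m = ln 2 / M) and registration even from 1 October 2015 to 31 August 2018. The onset hazard h is constant, continues for 28 days after stopping, and is set so that 20% have onset by last dose + 28 days: 1 − e^(−28h) · m/(m+h) = 0.20.

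**4. Patients affected by the missing limit.** Registration falls 33 to 1,098 days before 3 October 2018, a span of 1,065 days, so the expected number is 200 × (e^(−33m) − e^(−1098m)) / (1065m). For M = 30: m = 0.0231, and 200 × 0.467 / 24.6 = 3.8. For M = 180: m = 0.00385, and 200 × (0.881 − 0.015) / 4.10 = 42.2. These count all patients whose observation ends after 3 October; those without an event are somewhat fewer.

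**5. Effect on the curve.** Kaplan-Meier was run on large simulated cohorts with events counted to 31 October 2018, censoring once without and once with the same limit.

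**6. Onsets after the last dose.** P(onset on treatment) = h/(m+h). The share after the last dose is (0.20 − h/(m+h)) / 0.20, times 40 cases. For M = 30: h = 0.00326, h/(m+h) = 0.1236, share 38%, 15.3 cases. If the hazard halves after stopping, replace 28h by 14h.

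| Median treatment (days) | 30 | 60 | 90 | 180 |
|---|---|---|---|---|
| Patients of 200 affected | 4 | 11 | 19 | 42 |
| Day-100 incidence lower by (points) | 0.16 | 0.11 | 0.09 | 0.05 |
| Post-dose onsets of 40, hazard unchanged | 15 | 10 | 7 | 4 |
| Post-dose onsets of 40, hazard halved | 10 | 5.5 | 4 | 2 |

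The sampling standard deviation of day-100 incidence with 200 patients is about 2 to 5 points in the same simulation, so the shift is about 3% of it.

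**7. Liver tests (SAP 8.2.3.3 with Appendix 1, A1.1).** The onset value is the last one before the day of onset. The completion value is the one closest to the last dose, on or after it. Example: last dose day 60, tests on days 60 and 63, onset day 65. The onset value is day 63 and the completion value day 60, so the order is reversed. With a test on day 63 only, the two are the same test.

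**8. Collection in the 28 days, side by side.** Protocol 7.2.6 with 7.3.7 stops recording at the last dose for patients who stop. Protocol 9.2 and its extension point to 28 more days. The table in Protocol 9.1 places all non-serious events on the case report form and none on the expedited NIS form, which is the form SAP 8.2.3 cites. Section 9 treats the NIS form as part of the case report form. Protocol 9.3 adds that where causality is finally unknown "the safety event must be reported within 24 hours".

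**The case against.** The strongest reply to the censoring point is that the 31 October 2018 sentence heads SAP 8.2.3 and concerns the same window that 8.2.3.1 reuses, so one cut-off is probably intended for both. That is likely the intent, but the sentence limits events and says nothing about censoring dates, and a programmer could follow either reading. The small effect stands as an objection to the weight of the point. The group named in the censoring sentence is wrong under either reading.

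On classification, SAP 7 supplies 'unknown', and every patient has a completion or discontinuation status under Protocol 7.3.5. But 'unknown' covers only missing values, and a patient-level status does not say whether the event changed the treatment. The case report form may carry a suitable code; it is not among the documents.

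A reader might infer that non-serious events were not collected after the last dose and that the curve is therefore biased by several points. The documents do not support that. Protocol 9.2 covers every event type in the 9.1 table. Its extension applies to anyone dosed on the last observation day, which under 7.2.6 is nearly everyone. Section 9 makes the NIS form part of the case report form. Incomplete capture is only a possibility, and the documents give no capture rate from which to size it; with full capture there is no bias.

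Replacing the 28-day window by censoring at the last dose is also tempting. It would drop serious post-dose events from the curve, and such censoring may be informative if patients stop for evolving toxicity.

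**Conclusion.** The point holds and is minor. Two defects are clear from the text. The censoring rule omits the date limit placed on events and names the wrong event-free group. Onsets after the last dose are tabulated but fit none of the change-in-treatment levels.

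The effect on the curve is negligible: 0.05 to 0.16 points at day 100, given even registration and median treatment of 30 to 180 days. It would be larger if registration were concentrated near the end and treatment long, but nothing in the documents indicates that. The classification gap could touch about 4 to 15 of 40 hepatic cases with an unchanged hazard after stopping, which is an upper figure, and about 2 to 10 if the hazard halves.

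Crude proportions do not depend on the censoring rule, and SAP 4.1 treats all tests as exploratory, so no decision rests on these results. The provisions on collection after the last dose need reconciling; they do not establish that data are missing.

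**What to change.** 1. **Censoring (SAP 8.2.3.1).** Censor patients without the major investigation item in question at the earlier of observation end + 28 days and 31 October 2018.
2. **Change in treatment (SAP 8.2.3.1 and 8.2.3.3).** Add a level 'not applicable (onset after last dose)'. Show these onsets separately in the major-item tables, the discontinued-versus-not comparison and the liver-test summaries. Keep in the discontinued group any event recorded as the reason for discontinuation under Protocol 7.3.5.
3. **Collection window (secondary).** Reconcile Protocol 7.2.6, 7.3.7, 9.1 and 9.2 with SAP 8.2.3, and confirm from the case report form and its instructions that non-serious events were collected in the 28 days. If they were not, add on-treatment onset, censored at the last dose, as a sensitivity analysis beside the 28-day analysis and not in its place.

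**Cost.** A few lines of SAP text and minor programming with items already collected: onset date, last dose date, action taken and reason for discontinuation. The main discontinued-versus-not comparison loses a few cases to the new level, and the report must say how many.

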# 7.2.1. Inclusion criteria

- 1. Patients who have not developed invasive fungal infections at the time of initiation of administration of this product (patients with medical history of invasive fungal infections can be registered)
- 2. Patients with history of hematopoietic stem cell transplantation or patients who plan to receive hematopoietic stem cell transplantation

The indications and dosage and administration of this product are as follows. The latest package insert should be referred to when administering this product.

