# 7.2.6. Observation period

The observation period shall start on the day the administration of this product begins and ends on the day the administration is completed; provided that the patients will be followed until the last day of the investigation period as long as possible if the administration period prolongs.

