#### 7.3.3. Concomitant therapy

# 7.3.3.1. Concomitant medications for prophylaxis of invasive fungal infections, mediations listed in precautions for coadministration / contraindication for coadministration and immunosuppressants

The following information will be recorded for concomitant medications for prophylaxis of invasive fungal infections, concomitant medications for precautions for coadministration /contraindications for coadministration, and immunosuppressants from the initiation of administration of this product until the completion date of observation period.

- (1) Drug name (product name)
- (2) Daily dose
- (3) Route of administration
- (4) Administration period

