#### 7.5.2. Rationale for sample size

It was considered that the following evaluations were possible if the target sample size was set to be 200 patients in total; 100 patients each for children and adults.

Safety perspectives:

In the phase 3 study of prophylactic administration of Vfend in foreign patients with HSCT (study A1501073), the incidence of adverse reactions classified into the SOC of hepatobiliary disorders was 20.2% (47/233 patients). Of those, one patient was led to discontinuation of administration of this product. In the phase 3 study of secondary prophylactic administration of Vfend in foreign patients with HSCT (study A1501038), the incidence of adverse reactions classified into the SOC of hepatobiliary disorders was 24.4% (11/45 patients). Of those, two patients were led to discontinuation of this product. Also, in the clinical study of Vfend conducted in Japanese children (from 2 years old to under 15 years old) (study A1501096), the incidence of adverse reactions related to hepatic toxicity including abnormal hepatic function test values was 19.0% (4/21 patients). Of those, two patients were led to discontinuation of this product. Based on the above, the incidence of hepatic toxicity in patients administered this product for prophylaxis of invasive fungal infections was similar between Japanese and foreign patients and it was considered that such incidence was also similar between adults and children.

In the case where the number of patients to be collected for the special investigation for prophylactic administration of Vfend for invasive fungal infections is set to be 200 patients and the incidence of hepatic toxicity is presumed to be 20%, it is estimated that at least 31 patients with hepatic toxicity will be accumulated at a probability of about 95%. With the cumulation of this sample size, it was considered possible to compare and review the proportion of patients who discontinued the administration of this product with the clinical studies.

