4. HYPOTHESIS AND DECISION RULES

4.1. Statistical Hypothesis

Because this study is not a confirmatory investigation, the tests are considered as exploratory tests. The P value of test results will be evaluated as descriptive statistics. The significance level is not provided, but a threshold may be set afterwards for the purpose of screening.

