5.4. Subgroup Analysis

Subgroup analyses of safety and effectiveness will be performed for the following patient background factors and other factors. Levels in parentheses are levels of subgroups, and underlined levels are the reference for calculation of risk ratio and risk difference.

- Sex [male, female]
- Age (1) [<15 years, ≥ 15 years]
- Age (2) [<65 years, ≥65 years)
- Age (children 1) [newborns (<1 month after birth), infants (≥1 month to <1 year), younger children (≥1 to <7 years), children (≥7 to <15 years)]
- Age (children 2) [<2 years, ≥ 2 to <15 years]
- Hospitalized Status [inpatient, outpatient]
- Objective of treatment [primary prophylaxis (patients without history of fungal infection), secondary prophylaxis (patients with history of fungal infection), others]
- Type of transplantation [autograft, allogeneic full transplantation, allogeneic mini-transplantation]
- Source of transplantation [bone marrow, cord blood, peripheral stem cell]
- Occurrence of GVHD (graft versus host disease) [absent, present]
- Indication for transplantation¹ [leukemia, myelodysplastic syndrome, malignant lymphoma, myeloma, others]
- Severity of indication for transplantation [mild, moderate, severe]
- Hepatic dysfunction [absent, present]
- Severity of hepatic dysfunction [mild, moderate, severe]
- Renal dysfunction [absent, present]
- Severity of renal dysfunction [mild, moderate, severe]
- Past medical history [absent, present]
- Concurrent illness [absent, present]
- Congenital severe immunodeficiency² [absent, present]
- White blood cell count before administration [$<3000/\mu$ L, $\geq 3000/\mu$ L]
- Neutrophil count before administration [$<500/\mu$ L, $\geq 500/\mu$ L]
- Concomitant use of broad-spectrum antibiotics [absent, present]
- Use of contraindicated concomitant medications [absent, present]
- Use of concomitant medications requiring precautions for coadministration [absent, present]
- Concomitant use of immunosuppressants (other than steroids) [absent, present]
- Concomitant use of steroids [absent, present]
- Concomitant use of steroids or immunosuppressants other than steroids [absent, present]
- Concomitant use of other antifungal agents [absent, present]
- Prior treatment (antifungal agents administered for prophylaxis of invasive fungal infections)
 [absent, present]
- Long-term treatment [$\leq 180 \text{ days}$, $\geq 180 \text{ days}$]

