The number and proportion of patients with adverse drug reactions and major investigation items will be tabulated overall and by PT by presence or absence of actually used concomitant medications for each adverse drug reaction and major investigation item to evaluate the relationship of contraindicated concomitant medications, concomitant medications requiring precautions for coadministration, concomitantly used other antifungal agents, and concomitant immunosuppressants with adverse drug reactions considered as major investigation items. However, medications started to be used after the day of the last onset of the event during the observation period + follow-up period (28 days) will be excluded from tabulation.

In addition, the number and proportion of patients with adverse drug reactions and major investigation items will be tabulated by PT by presence or absence of each actually used concomitant medication for

each adverse drug reaction and major investigation item to evaluate the relationship of contraindicated concomitant medications, concomitant medications requiring precautions for coadministration, concomitantly used other antifungal agents, and concomitant immunosuppressants with adverse drug reactions considered as major investigation items. However, medications started to be used after the day of the last onset of the event during the observation period + follow-up period (28 days) will be excluded from tabulation.

• The adverse drug reactions by patients of included/excluded in the safety analysis set

In patients for whom the case report form was collected, the listing of adverse drug reactions in patients excluded from the safety analysis set will be prepared. The number of patients with events will be tabulated by SOC and PT.

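### Concomitant-drug tables: SAP 8.2.3.1 cuts exposure at a date only patients with the event have, and SAP 5.4 sets no exposure window, so both comparisons can be biased for drugs started after Day 1

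*SAP*

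**What the plan says.** **SAP 8.2.3.1** (relationship between concomitant medications and ADRs) tabulates the number and proportion of patients with ADRs and major investigation items by presence or absence of the drugs used. It covers contraindicated drugs, drugs needing precautions, other antifungals and immunosuppressants, and its stated purpose is to evaluate their relationship with ADRs. Both paragraphs exclude "medications started to be used after the day of the last onset of the event during the observation period" plus the 28-day follow-up. Neither states a cut for patients without the event.

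**SAP 5.4** lists the same kinds of drug as two-level factors, for example "Concomitant use of steroids [absent, present", without dates. Other entries in that list are anchored in time, such as "White blood cell count before administration". Appendix 1 defines timing for laboratory tests only.

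**SAP 8.2.3.4** cross-tabulates any ADR by each 5.4 factor, with risk ratio and risk difference under 8.1.3. Two exceptions apply: the combined steroid/immunosuppressant factor gets no ratios, and 8.1.3 gives none when a compared category has 5 or fewer patients. Under 8.2.3.5, a risk ratio of at least 2 or at most 0.5 triggers a further table.

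**Protocol.** Concomitant drugs, with their administration periods, are recorded "from the initiation of administration of this product until the completion date of observation period" (7.3.3.1). Observation "ends on the day the administration is completed" (7.2.6), so its length differs between patients. Eligibility extends to "patients who plan to receive hematopoietic stem cell transplantation" (7.2.1), so drug starts after Day 1 are possible by design.

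**The concern.** The two tables fail for different reasons.

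- **8.2.3.1.** A patient with the event can be counted as exposed only if the drug began by the last onset. An event-free patient can be counted as exposed by a start at any time in observation. The second group has more time to qualify, which pushes the exposed proportion with ADRs down (immortal-time bias).
- **5.4 and 8.2.3.4.** With no window, a drug begun after the ADR, or because of it, counts as exposure. Patients treated longer also have more time for both a drug start and an ADR, which pushes the ratio up. If the ADR ends treatment, that patient has less time to start a drug, which pushes it down.

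At stake is the objective on factors affecting safety, for which interacting drugs are an obvious candidate. Neither bias shrinks with more patients. A real harm can be understated, and the report gives the reader no way to tell an artefact from a signal.

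**Working it through.** **1. The plan's own figure.** The documents give no number for these tables. The nearest is the hepatic count in Protocol 7.5.2: 200 patients, 20% risk, at least 31 cases with probability about 95%. The exact binomial gives P(X ≥ 31) = 0.957, so it reproduces. Expected cases: 200 × 0.20 = 40.

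**2. Inputs.** From the documents: 20% risk, and hepatic ADRs leading to discontinuation in 1/47 ("Of those, one patient was led to discontinuation of administration of this product"), 2/11 and 2/4, pooled as 5/62 = 8%. Drug-start rates, treatment lengths, onset pattern and recurrence are not given. They are assumptions below.

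**3. A case that can be checked by hand.** Drug with no effect; everyone followed 90 days; no discontinuation; constant hazards; 20% on the drug at Day 1; 40% of the rest start by day 90.

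- The hazards of event and start are in the ratio −ln 0.8 : −ln 0.6 = 0.2231 : 0.5108. The event share is 0.2231/0.7340 = 0.304.
- Among those not on the drug at Day 1, P(event before any start) = 0.304 × (1 − 0.8 × 0.6) = 0.158, and P(start, then event) = 0.200 − 0.158 = 0.042.
- Events classed exposed: 0.2 × 0.2 + 0.8 × 0.042 = 0.0735. Events classed unexposed: 0.8 × 0.158 = 0.1265.
- Event-free exposed: 0.8 × (0.2 + 0.8 × 0.4) = 0.416. Event-free unexposed: 0.8 × 0.48 = 0.384.
- **8.2.3.1:** 0.0735/(0.0735 + 0.416) = 15.0% against 0.1265/(0.1265 + 0.384) = 24.8%, ratio 0.61.
- **5.4:** any use is 52% with or without the event, so 20% against 20%, ratio 1.00.

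With treatment length uniform over 7 to 180 days instead, simulation gives 17.0% against 22.9% under 8.2.3.1 (0.74) and 22.8% against 17.3% under 5.4 (about 1.3).

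**4. Base-case simulation.** One million patients per setting, drug with no effect, 20% risk, 5/62 discontinuation, later starts 0.006 per day. ADRs count to treatment end plus 28 days and drug starts to treatment end. Length is 90 days, or exponential with median 60. Early-clustered means a 20-fold hazard in the first 14 days. Entries are the ratio of ADR proportions, exposed to unexposed. 8.2.3.1 itself plans proportions only.

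| Treatment length | Onset | On drug at Day 1 | 8.2.3.1 | 5.4 |
|---|---|---|---|---|
| Fixed | Constant | 10% | 0.63 | 0.96 |
| Fixed | Constant | 80% | 0.81 | 0.98 |
| Fixed | Early-clustered | 10% | 0.34 | 0.93 |
| Fixed | Early-clustered | 80% | 0.68 | 0.97 |
| Variable | Constant | 10% | 1.00 | 1.63 |
| Variable | Constant | 80% | 1.00 | 1.30 |
| Variable | Early-clustered | 10% | 0.46 | 1.10 |
| Variable | Early-clustered | 80% | 0.77 | 1.04 |

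Independent runs agree to within about 0.02. In the variable-length, constant-hazard rows the two influences on 8.2.3.1 cancel.

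**5. Sensitivity.**

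- If 25% of cases start the drug because of the ADR and half recur: 0.54–1.21 under 8.2.3.1 and 1.17–2.03 under 5.4.
- At 50% discontinuation (the paediatric 2/4): 5.4 gives 0.62–1.29 and 8.2.3.1 is unchanged.
- At 60% ADR risk: 0.51–1.00 and 0.96–1.32.
- With a true hazard ratio of 3, 8.2.3.1 shows 0.85–2.55.

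**6. One rule for everyone.** Exposure defined as use on Day 1 gives 1.00–1.01 in every base-case setting with no effect. Under a true hazard ratio of 3 it gives 1.65–2.24, so it dilutes a real effect.

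**The case against.** **Exploratory status.** SAP 4.1 states that "the tests are considered as exploratory tests", 8.2.3.1 gives only counts and proportions, a screen flag leads only to another table, and by-patient listings are planned. This limits the consequence. It does not remove it, because a descriptive proportion carries the same bias.

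**The one-sided cut is partly inferred.** The SAP does not say that event-free patients are uncut, and Protocol 7.3.3.1 says what is recorded, not what is counted. A table restricted to patients with each reaction would have no asymmetry. Still, a comparison by presence or absence of a drug, meant to evaluate a relationship, is ordinarily read as covering all patients, and the text offers no cut date for those without the event.

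**Two stronger readings are tempting.** A reader might infer that a drug with no effect will generally look protective in one table and harmful in the other. The base case does not show that: with fixed length 5.4 is never above 1, with variable length and constant hazard 8.2.3.1 is unbiased, and in the remaining rows 5.4 is close to 1. A clear split needs particular treatment lengths or drug starts prompted by the ADR, and the documents give neither.

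A reader might also infer that such drugs would often trip the screen at 200 patients. In one favourable setting (variable length, constant hazard, 10% Day-1 use, 20% risk) they do so in 23% of datasets, against 2% without timing bias. With early-clustered onset it is 3% against 2%, and at 43% risk 2.5% against 0.1%. The screen uses any ADR, whereas 20% is the hepatic figure alone.

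**Exemptions.** The combined steroid/immunosuppressant factor and categories of 5 or fewer patients never reach the screen. The exemption is most naturally read as that combined factor only, leaving the separate steroid and immunosuppressant factors in.

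**Conclusion.** The point stands in moderate form. As written, 8.2.3.1 treats patients with and without the event differently, and 5.4 leaves exposure undated. For drugs started after Day 1, each can give a ratio away from 1 when the drug does nothing.

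The size rests on assumed start rates and treatment lengths. At 20% risk and 8% discontinuation it is about 0.34 to 1.00 under 8.2.3.1, mostly protective, and about 0.93 to 1.63 under 5.4: near 1 when treatment length is equal, above 1 when it varies, and higher with reactive starts. That a bias arises follows from the text; its magnitude, and its direction in 5.4, depend on those inputs. Opposite directions are possible, not general. Drugs that all users take from Day 1 are unaffected.

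The consequence is for interpretation, not for any formal test. The change should be made before the final analysis.

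**What to change.** 1. **One exposure rule.** In the drug-class tables of 8.2.3.1 and for the concomitant-drug factors in 5.4, define exposure as use on Day 1 of Vfend for every patient. State the downside: later starters sit in the unexposed group and dilute a real effect.
2. **Label the rest.** Keep the any-use tables and the by-drug, by-PT tables as descriptive counts. Do not pass undated drug factors to the 8.2.3.5 screen or read them as association. Apply the same label in 8.2.4.4, where these factors enter the effectiveness subgroups (not simulated here).
3. **Optional, where events allow.** For drug classes against overall ADRs and hepatic toxicity, add a time-dependent analysis: unexposed before the drug starts, follow-up to first onset, stratified by time since Vfend start or a Cox model with time-varying exposure, with 95% CI. Crude patient-time is not enough, since with 20-fold early hazard it gives 0.38–0.81 under no effect. Precision is poor: with about 40 cases and no effect, the estimate ranges over about 0.41–2.25.
4. **Reconcile the windows.** Protocol 7.2.6 ends observation when treatment ends, Protocol 9.2 says it must include at least 28 days after the last dose, Protocol 7.3.3.1 ties drug recording to the end of observation, and SAP 8.2.3 treats the 28 days as a separate follow-up. State whether concomitant drugs are recorded in those 28 days.

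Cost: items 1, 2 and 4 need SAP or protocol wording and light reprogramming. Item 3 needs moderate programming. Apart from what item 4 settles, no new data are required, because administration periods are already collected.
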